## 5.1 Table of Study-Related Interventions

| Assessments  | Pre-Enrollment Screening                           | Salvage Induction Cycle 1   |                  |                  |                  |                  |                  |                  |                  |
|--|--|---|------------------|------------------|------------------|------------------|------------------|------------------|------------------|
|  |  | Day 1   | Day 2            | Day 3            | Day 4            | Day 5            | Day 6            | Day 7            | Day 8            |
| Treatment with CPI-613   |  | ✓   | ✓                | ✓                | ✓                | ✓                |                  |                  |                  |
| Treatment with Cytarabine  |  |   |                  | ✓                | ✓                | ✓                |                  |                  |                  |
| Treatment with Mitoxantrone  |  |   |                  | ✓                | ✓                | ✓                |                  |                  |                  |
| Medical history    | ✓  |   |                  |                  |                  |                  |                  |                  |                  |
| Physical exam  and vital signs   | ✓                                      | ✓   | ✓    | ✓    | ✓    | ✓    |                  |                  |                  |
| Pregnancy test for woman of child-bearing potential  | ✓  |   |                  |                  |                  |                  |                  |                  |                  |
| TTE, MUGA or MRI   | ✓  |   |                  |                  |                  |                  |                  |                  |                  |
| ECOG performance status  | ✓  |   |                  |                  |                  |                  |                  |                  |                  |
| Evaluation of symptoms & medications   | ✓  |   |                  |                  |                  |                  |                  |                  |                  |
| Clinical chemistry  , hematology & coagulation    | ✓  | ✓   | ✓  | ✓  | ✓  | ✓  | ✓  | ✓  | ✓  |
| Creatinine, BUN  |  | ✓    | ✓   | ✓   | ✓   | ✓   | ✓   | ✓   | ✓   |
| Anti-Tumor Efficacy (i.e., imaging for granulocytic sarcoma, bone marrow biopsy for AML)   | Obtained within 2 weeks prior to the first dose.   | Obtained on day 14 of cycle 1.  |                  |                  |                  |                  |                  |                  |                  |
| Optional blood, urine and plasma samples, as well as bone marrow via biopsy  for possible testing of biomarkers, predictors of biological responses, toxicity, genotype vs. drug response relationship, etc. | Obtained within 2-4 weeks prior to the first dose. | Blood sample to be obtained prior to and following the dose of CPI-613 at 2, 4, and 6 hours from end of CPI-613 infusion on day 1 and bone marrow sample to be obtained on day 14 of Cycle 1. Bone marrow samples may be collected +/- 1-2 days if falls on a weekend or holiday. Optional urine samples will be collected from the first void after the first infusion of CPI-613. Details of the collection will be recorded on Appendix G. |                  |                  |                  |                  |                  |                  |                  |

 Height, weight are also determined during pre-enrollment screening. Renal function will be assessed utilizing the Cockcroft-Gault formula. The Response Criteria will be assessed by standard criteria (Blood. 2010;115:453-474). Vital signs will be performed immediately after CPI-613 administration and the patient only re-examined if clinically indicated. These tests are performed within 24 hrs prior to dosing. Only the results of the creatinine are needed before CPI-613 is dosed. For Day 1 of Treatment Cycle 1, the pre-enrollment test results can be used for all labs except creatinine which must be rechecked 24 hours prior to dosing. The frequency of assessment beyond Cycle 1 is:

- For medical history, physical exam and vital signs, ECOG PS, evaluation of symptoms and medications, they are assessed within 5 days of the next cycle doses.
- Clinical chemistry and hematology are assessed on day 5 of each cycle (or day 3 if short dosing cycle is given).

 Bone Marrow via biopsy will only be collected if deemed appropriate by physician Creatinine and BUN to be checked within 24 hours of every dose and at 24, 48 and 72 hours post last dose of CPI-613, mitoxantrone, and cytarabine (i.e., days 6, 7, and 8) Coagulation (PT/PTT) to be completed Day 1 and weekly during Cycle 1.

| Assessments   | Salvage Consolidation Cycle 1 and 2  |                |                |       |       |       |       |       |
|---|--|----------------|----------------|-------|-------|-------|-------|-------|
|   | Day 1  | Day 2          | Day 3          | Day 4 | Day 5 | Day 6 | Day 7 | Day 8 |
| Treatment with CPI-613  | ✓  | ✓              | ✓              |       |       |       |       |       |
| Treatment with Cytarabine   |  | ✓              | ✓              |       |       |       |       |       |
| Treatment with Mitoxantrone   |  | ✓              | ✓              |       |       |       |       |       |
| Medical history   | ✓    |                |                |       |       |       |       |       |
| Physical exam  and vital signs    | ✓    | ✓  | ✓  |       |       |       |       |       |
| Pregnancy test for woman of child-bearing potential   | ✓  |                |                |       |       |       |       |       |
| TTE, MUGA or MRI  | ✓   |                |                |       |       |       |       |       |
| ECOG performance status   | ✓  |                |                |       |       |       |       |       |
| Evaluation of symptoms & medications  | ✓  |                |                |       |       |       |       |       |
| Clinical chemistry  and hematology   | ✓    | ✓  | ✓  |       |       |       |       |       |
| Creatinine, BUN   | ✓  | ✓              | ✓              |       |       |       |       |       |
| Anti-Tumor Efficacy (i.e., imaging for granulocytic sarcoma, bone marrow biopsy for AML)    | Obtained upon completion of all planned consolidation therapy.   |                |                |       |       |       |       |       |
| Optional blood and plasma samples, as well as bone marrow via biopsy  for possible testing of biomarkers, predictors of biological responses, toxicity, genotype vs. drug response relationship, etc. | Blood sample to be obtained prior to and following the dose of CPI-613 at 2, 4, and 6 hours from end of CPI-613 infusion on day 1 and bone marrow sample to be obtained at the end of planned consolidation therapy. Bone marrow samples may be collected +/- 1-2 days if falls on a weekend or holiday. |                |                |       |       |       |       |       |

 Height, weight are determined during pre-enrollment screening.  
 Renal function will be assessed utilizing the Cockcroft-Gault formula.  
 The Response Criteria will be assessed by standard criteria (Blood. 2010;115:453-474).  
 Vital signs will be performed immediately after CPI-613 administration and the patient only re-examined if clinically indicated.  
 These tests are performed within 24 hrs prior to dosing. Only the results of the creatinine are needed before CPI-613 is dosed.  
 The frequency of assessment is:  
- For medical history, physical exam and vital signs, ECOG PS, evaluation of symptoms and medications, they are assessed within 5 days of the next cycle doses.  
 Bone Marrow via biopsy will only be collected if deemed appropriate by physician  
 Creatinine and BUN to be checked within 24 hours of every dose of CPI-613  
 TTE/MUGA/Cardiac MRI can be obtained within 2 weeks of consolidation as long as no other cardiac toxins have been administered. Prior to cycle 2 of consolidation TTE/MUGA/Cardiac MRI is at the discretion of the treating physician

| Assessments   | Maintenance Therapy  |                |                |                |                |       |       |       |
|---|--|----------------|----------------|----------------|----------------|-------|-------|-------|
|   | Day 1  | Day 2          | Day 3          | Day 4          | Day 5          | Day 6 | Day 7 | Day 8 |
| Treatment with CPI-613  | ✓  | ✓              | ✓              | ✓              | ✓              |       |       |       |
| Medical history   | ✓    |                |                |                |                |       |       |       |
| Physical exam  and vital signs    | ✓    | ✓  | ✓  | ✓  | ✓  |       |       |       |
| Pregnancy test for woman of child-bearing potential   | ✓  |                |                |                |                |       |       |       |
| ECOG performance status   | ✓    |                |                |                |                |       |       |       |
| Evaluation of symptoms & medications  | ✓    |                |                |                |                |       |       |       |
| Clinical chemistry  and hematology   | ✓    | ✓  | ✓  | ✓  | ✓  |       |       |       |
| Creatinine, BUN   | ✓  | ✓              | ✓              | ✓              | ✓              |       |       |       |
| Anti-Tumor Efficacy (i.e., imaging for granulocytic sarcoma, bone marrow biopsy for AML)    | Obtained upon completion of every fourth cycle.  |                |                |                |                |       |       |       |
| Optional blood and plasma samples, as well as bone marrow via biopsy  for possible testing of biomarkers, predictors of biological responses, toxicity, genotype vs. drug response relationship, etc. | Blood sample to be obtained prior to and immediately following the dose of CPI-613 on day 1 and bone marrow sample to be obtained at the end of planned maintenance therapy. Bone marrow samples may be collected +/- 1-2 days if falls on a weekend or holiday. |                |                |                |                |       |       |       |

 Height, weight are determined during pre-enrollment screening.  
 Renal function will be assessed utilizing the Cockcroft-Gault formula.  
 The Response Criteria will be assessed by standard criteria (Blood. 2010;115:453-474).  
 Vital signs will be performed immediately after CPI-613 administration and the patient only re-examined if clinically indicated.  
 These tests are performed within 24 hrs prior to dosing. Only the results of the creatinine are needed before CPI-613 is dosed.  
 The frequency of assessment for cycles after cycle 1 is:  
- For medical history, physical exam and vital signs, ECOG PS, evaluation of symptoms and medications, they are assessed within 7 days of the next cycle doses.  
 Bone Marrow via biopsy will only be collected if deemed appropriate by physician.  
 Creatinine and BUN to be checked within 24 hours of every dose of CPI-613.

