## SCHEMA

This is a Pilot open label trial to establish the feasibility of CPI-613 in combination with high dose cytarabine and mitoxantrone:

*Salvage Induction:* CPI-613 at doses of 1,500 mg/m^2/day will be given over 2 hours on days 1-5. Cytarabine will be given at 3gm/m^2 for age <60 or 1.5 gm/m^2 for age >60 in 500 mL NS over 3 hours every 12 hours for 5 doses starting on day 3. Mitoxantrone will be given at 6mg/m^2 daily for 3 doses given in 50 mL NS over 15 minutes after 1st, 3rd and 5th doses of Cytarabine. A day 14 marrow will be obtained to assess disease response. If there is a response to therapy but residual disease remains patients may receive either a repeated courses identical to the above or a shortened 3 day course with CPI-613 on days 1-3, cytarabine starting on day 2 for 3 total doses and Mitoxantrone after 1st and 3rd doses at the discretion of the treating physician.

There will be 20 patients recruited at a CPI-613 dose of 500mg/m^2/day following the same treatment guidelines outlined above. Individuals recruited to this dose level of CPI-613 will remain on this dose level for consolidation and maintenance therapy.

*Salvage Consolidation:* All responding patients are eligible for consolidation therapy with up to 2 cycles of the shortened 3 course of CPI-613 (same dose as induction cycle), high dose cytarabine and mitoxantrone. Responding patients can be removed from trial at any time to receive a stem cell transplant at the discretion of the treating physician. Patients can move to maintenance following 1, 2 or no cycles of consolidation at the discretion of the treating physician.

*Maintenance Therapy:* Any patient who has completed all planned consolidation therapy (i.e. 0, 1 or 2 cycles) and is not eligible for, faces a significant delay or refuses a stem cell transplant may receive maintenance therapy with CPI-613 at a dose of 2,500 mg/m^2/day over 2 hours on days 1-5 of a 28 day cycle. Patients treated during induction and consolidation at the 500 mg/m^2 dose will receive that dose during maintenance therapy. Patients may continue on maintenance therapy until evidence of disease progression or occurrence of intolerable side effects.

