## **5.6 Study Procedures – Assessment of Safety, Plasma Concentration, and Possible Anti-Tumor Efficacy**

*Safety Assessment:* The safety of CPI-613 will be assessed based on:

- physical exams
- vital signs
- clinical pathology

- clinical chemistry
- renal function
- hematology

For physical exams and vital signs, they are to be performed during screening (performed within 2 weeks prior to treatment with CPI-613) and after CPI-613 administration in Cycle 1. Beyond Cycle 1, physical exam and vital signs will be assessed within 5 days of the next cycle doses.

For clinical pathology (i.e., clinical chemistry, renal function, hematology and coagulation), they are to be performed during screening (performed within 2 weeks prior to treatment with CPI-613), and within 24 hrs prior to dosing. Creatinine results within the last 24 hours must be reviewed prior to CPI-613 dosing. For Day 1 of Treatment Cycle 1, pre-dose assessments of clinical pathology are not needed because the pre-enrollment results can be used. Beyond cycle 1, laboratory assessments will be assessed on at least day 1 and 5 of each cycle rather than prior to beginning each cycle.

For left ventricular ejection fraction assessments, they are evaluated during screening and prior to consolidation therapy. Additional assessments can be made at the discretion of the treating physician.

*Anti-Tumor Efficacy – A Secondary Endpoint:* Baseline anti-tumor efficacy (i.e., bone marrow biopsy) will be obtained within 2 weeks prior to the first dose of treatment cycle 1. Follow-up anti-tumor efficacy will be obtained on day 14 of cycle 1. In patients treated with additional treatment cycles beyond Cycle 1, anti-tumor efficacy will be assessed upon count recovery (defined as ANC>1000, freedom from RBC transfusions and platelets>100k) or day 42 from the first day of the cycle whichever comes first. Anti-tumor efficacy assessment will also be based on investigator and institutional routine monitoring of the disease progression of the patients, together with baseline evaluations performed prior to treatment with CPI-613. During maintenance therapy anti-tumor efficacy will be assessed after every 4th cycle.

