### **6.0 Dosing Delays/Dose Modifications for CPI-613**

The occurrence of Grade 1 toxicity does not generally require dose modification for subsequent doses for that patient. However, if Grade 2 non-hematologic, non-infectious toxicity develops attributed as at least probably related to CPI-613, treatment can resume only after the Grade 2 toxicity has been reduced to Grade 1 or below, and the dose level for subsequent doses for that patient will be reduced by 25% of the dose at which such Grade 2 toxicity occur. If Grade 3 or 4 non-hematologic, non-infectious toxicity develops, dosing of that patient will be withheld and the patient shall be monitored for recovery from, and reversibility of, such Grade 3 or 4 toxicity. To resume treatment for a patient who has had Grade 3 or 4 toxicity, the Grade 3 or 4 toxicity must be reduced to Grade 1 or below, and the dose level for subsequent doses for that patient will be reduced

to 50% of the dose at which such Grade 3 or 4 toxicity occur. If the reduced dose of CPI-613 results in no toxicity, patients may be dose escalated to the prior dose at the discretion of the treating physician.

Dose adjustments during maintenance therapy will be done as described above with the addition that should patients experience hematologic toxicity  $\geq$  Grade 2 attributed to CPI-613 the next dose of maintenance therapy must be held until the Grade 2 toxicity has been reduced to Grade 1 or below, and the dose level for subsequent doses for that patient will be reduced by 25% of the dose at which such Grade 2 toxicity occurred. If Grade 3 or 4 hematologic toxicity develops, dosing of that patient will be withheld and the patient shall be monitored for recovery from, and reversibility of, such Grade 3 or 4 hematologic toxicity. To resume treatment for a patient who has had Grade 3 or 4 hematologic toxicity, the Grade 3 or 4 hematologic toxicity must be reduced to Grade 1 or below, and the dose level for subsequent doses for that patient will be reduced to 50% of the dose at which such Grade 3 or 4 hematologic toxicity occurred. If the reduced dose of CPI-613 results in no toxicity, patients may be dose escalated to the prior dose at the discretion of the treating physician.

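### From maintenance cycle 2 onward, the day 1 CPI-613 dose can be given on a creatinine result alone, with the blood count that informs the mandatory hematologic hold still unread

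*Combined protocol and SAP*

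**What the plan says.** Maintenance CPI-613 is given "over 2 hours on days 1-5 of a 28 day cycle" (Schema). For this phase alone, Section 6.0 adds a hematologic rule. If hematologic toxicity of grade 2 or more is "attributed to CPI-613 the next dose of maintenance therapy must be held until the Grade 2 toxicity has been reduced" to grade 1 or below, the dose afterwards "will be reduced by 25% of the dose at which such Grade 2 toxicity occurred". After grade 3 or 4, dosing is withheld, and on recovery the dose "will be reduced to 50% of the dose at which such Grade 3 or 4 hematologic toxicity occurred".

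The maintenance table in Section 5.1 ticks chemistry and hematology, as a single row, on days 1 to 5. Each tick carries footnote 5, which places the draw within 24 hours before dosing and then says: "Only the results of the creatinine are needed before CPI-613 is dosed".

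Section 5.6 takes the same line: "Creatinine results within the last 24 hours must be reviewed prior to CPI-613 dosing". It adds that beyond cycle 1 laboratory tests are "assessed on at least day 1 and 5 of each cycle rather than prior to beginning each cycle".

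**The concern.** A hold triggered by a blood count works only if the count is seen before the dose it is meant to stop. Here the schedule tells staff that creatinine is enough to release the dose, while Section 6.0 makes continued dosing depend on hematologic grade. A site that follows the schedule to the letter can give day 1 of a new maintenance cycle at full dose to a patient whose count, drawn hours earlier, would have called for a hold and a reduction. What is at stake is patient safety. The point does not depend on any effect on the primary analysis.

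**Working it through.** The plan states no figure to reproduce. The check sets the texts side by side and adds schedule and dose arithmetic.

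**Does any other text require the count to be read before the dose?**

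| Place | What it covers | Requires the count before dosing? |
|---|---|---|
| 5.1 maintenance, footnote 5 | Chemistry and hematology drawn within 24 h; creatinine result needed | No |
| 5.1 maintenance, footnote 7 | History, exam, vital signs, ECOG status, and "evaluation of symptoms and medications, they are assessed within 7 days of the next cycle doses" | No; none is a count |
| 5.1 maintenance, footnote 10 | Creatinine and BUN | No |
| 5.5 | ANC threshold for optional loperamide | No; governs the premedication only |
| 5.6 | Creatinine review; labs on at least days 1 and 5 | No |
| 6.0 | Hold and reduction once toxicity is identified | Does not say when the count must be read |

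The maintenance hematology row also cites a footnote 11 that is not printed under that table. The footnotes with that number in the induction and consolidation tables concern coagulation and cardiac imaging. I place no weight on this.

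**Why maintenance in particular.** The creatinine-only sentence appears under all three tables. In induction and consolidation, Section 6.0 modifies CPI-613 only for non-hematologic, non-infectious toxicity, so the sentence conflicts with no hematologic hold there. Only in maintenance does it meet one.

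**Why day 1 of cycle 2 onward.** These are nominal days, using the maintenance table, which has the fullest schedule in the documents.

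- Day 1 of the next cycle = day 28 + 1 = day 29.
- Last other scheduled count: day 5, drawn before the fifth dose. Interval = 29 − 5 = 24 days.
- Days 6 to 28 with no scheduled count = 28 − 5 = 23 days.

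The day 1 count is therefore the first scheduled count after a completed five-day course. At maintenance cycle 1 the rule has least force, because no maintenance course has yet been given.

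**Dose at issue** (2,500 mg/m², or 500 mg/m² for the 500 mg/m² cohort; Section 5.0).

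| | 2,500 mg/m² | 500 mg/m² |
|---|---|---|
| Cycle total (5 doses) | 5 × 2,500 = 12,500 | 5 × 500 = 2,500 |
| One dose as a share of the cycle | 2,500 / 12,500 = 20% | 500 / 2,500 = 20% |
| Permitted on day 1 if the hold criterion is met | 0 | 0 |
| On resuming after grade 2 | 0.75 × 2,500 = 1,875 | 0.75 × 500 = 375 |
| On resuming after grade 3–4 | 0.50 × 2,500 = 1,250 | 0.50 × 500 = 250 |

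**How often the point arises.** A patient who completes the three cycles counted in the primary endpoint (Section 10.0) starts 3 − 1 = 2 cycles after the first, and so passes this point twice.

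**The case against.** The strongest reply is that Section 6.0 already governs. Footnote 5 is a generic sentence naming the routine release test. It waives nothing, and an investigator who honours Section 6.0 would look at a count drawn within the previous 24 hours. That is how a careful site would act. But Section 6.0 binds only once toxicity is known, and two explicit pre-dose instructions say that creatinine suffices. The hold cannot act on a result nobody has read.

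A second reply is that counts are probably seen more often than the table shows. Section 5.6 says at least days 1 and 5 and refers to routine disease monitoring, and Section 9.1 uses blood counts to assess disease status. This stands in part: unscheduled counts may well exist, and the 24 days is the gap between scheduled draws only. None of these texts fixes a draw date or a dosing condition.

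Third, the consequence may be rare. Section 1.4 reports no clinically evident myelosuppression from CPI-613. The grade 2 hold requires attribution to CPI-613, and a patient in CRi after cytarabine and mitoxantrone may have a low count for other reasons. This stands as a limit on frequency. It does not remove the need to see the count, since neither grade nor attribution can be judged without it.

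Finally, footnote 5 sits on days 2 to 5 as well, so limiting the exposure to one dose assumes that the day 1 result is read before the day 2 dose. That is correct, and the verdict states it as an assumption.

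**Conclusion.** The concern holds. The maintenance schedule releases CPI-613 on creatinine alone, while Section 6.0 imposes a mandatory hematologic hold, and no text requires the count to be read before the dose. The exposure is about one unreduced day 1 dose per affected cycle, 20% of the planned cycle dose, where Section 6.0 would allow none that day. This rests on three assumptions: the maintenance table is followed as written, no unscheduled count has already revealed the toxicity, and the day 1 result is acted on before day 2. The documents give no rate of CPI-613-attributed cytopenia in maintenance, so no number of affected patients is claimed and few may be. The inconsistency should be fixed because the remedy is cheap and the rule it protects is mandatory.

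**What to change.** Amend maintenance footnote 5 in Section 5.1, and Section 5.6 to match, along these lines: *Before day 1 of each maintenance cycle after the first, the CBC with differential already drawn, as well as the creatinine, must be reviewed against Section 6.0.* For maintenance, also delete the closing words of the Section 5.6 sentence on laboratory timing that set testing apart from the period before a cycle begins.

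With the day 1 result known before the day 2 dose, the wording for days 2 to 5 can stay as it is. No test is added. The cost is two text edits and a wait of some hours for the CBC on day 1 of maintenance cycles after the first.
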